#### **10.2.2.4 Pittsburgh Insomnia Rating Scale (PIRS-20)**

The PIRS-20 is the short version of the original PIRS, both copyrighted by the University of Pittsburgh. The original PIRS is a 65-scale item, widely used instrument in clinical and research practice. It was designed to rate the severity of insomnia in clinical trials and clinical practice. Domains of the PIRS-20 include subjective distress (12 items), subjective sleep parameters (4 items) and quality-of-life (4 items). The recall period of the PIRS-20 is the past 7 days. The PIRS-20 total score is the sum of all items and ranges from 0 (good sleep) to 60 (bad sleep). The PIRS-20 should be administered following the WHODAS at Visit 2 and Visit 3. Administration time: approximately 5-10 minutes.

#### **10.2.2.5 Repeatable Battery for the Assessment of Neuropsychological Status Update (RBANS Update)**

The Repeatable Battery for the Assessment of Neuropsychological Status (RBANS) was developed for the dual purposes of identifying and characterizing abnormal cognitive decline in the older adult and as a neuropsychological screening battery for younger patients. It is widely used in both clinical contexts and clinical trials. While easily tolerated by patients and easily administered, it is also psychometrically robust and sensitive in the detection of even mild expressions of cognitive impairment. The entire battery takes less than 30 minutes to administer, and yields scaled scores for five cognitive domains, known as Index Scores). These domains include Immediate Memory (List Learning and Story Memory), Visuospatial/Constructional (Figure Copy and Line Orientation), Language (Picture Naming and Semantic Fluency), Attention (Digit Span and Coding), and Delayed Memory (List Recall, List Recognition, Story Memory, and Figure Recall). The RBANS utilizes parallel forms, ideal for measuring change over time, and takes approximately 30 minutes to administer.

#### **10.2.2.6 Trail Making Tests A & B ([TMT-A & TMT-B] visual scanning speed/visual attention)**

Trail Making Tests (TMT) has been extensively used in neuro-psychological assessment. The Trail Making Test A (TMT-A) involves visual, conceptual, and visio-motor tracking. TMT-A requires primarily perceptual-motor speed, visual scanning, attention, and numeric sequencing. The Trail Making Test B (TMT-B) is a task of visual, conceptual, and visio-motor tracking which requires primarily perceptual-motor speed, visual scanning, attention, working memory and secondarily the ability to shift conceptually between numerical and alphabetical order. TMT-B is administered according to standard procedures. Both parts of the Trail Making Test consist of 25 circles distributed over a sheet of paper. In Part A, the circles are numbered 1 – 25, and the patient should draw lines to connect the numbers in ascending order. In Part B, the circles include both numbers (1 – 13) and letters (A – L); as in Part A, the patient draws lines to connect the circles in an ascending pattern, but with the added task of alternating between the numbers and letters (i.e., 1-A-2-B-3-C, etc.). The patient should be instructed to connect the circles as quickly as possible, without lifting the pen or pencil from the paper. The patient is timed as he or she connects the “trail.” If the patient makes an error, it should be pointed out immediately and patient is allowed to correct it. Errors affect the patient’s score only in that the correction of errors is included in the completion time for the task. Maximum time given for TMT A is 150 seconds and for TMT B is 300 seconds. Results for both TMT A and TMT B are reported as the number of seconds required to complete the task; therefore, higher scores reveal greater impairment. Although trail making tests are very simple, they have been hypothesized to reflect a wide variety of cognitive processes including attention, visual search, and scanning, sequencing, and shifting, psychomotor speed, abstraction, flexibility, ability to execute and modify a plan of action, and ability to maintain two trains of thought simultaneously.

Administration time: approximately 5-10 minutes. Normative data information are available.

#### **10.2.2.7 Clinician Global Impression of Improvement (CGI-I)**

The CGI-I measures change since initiating a medication and is assessed on a 7-point Likert-type scale ranging from very much improved (1) to very much worse (7). The CGI-I will be

administered at Visits 3 and 4 after the administration of the PIRS-20. Administration time: approximately 1 minute.

### 10.2.3 Adverse Events

An AE is any untoward sign, symptom or medical condition occurring at any time after the patient receives his/her first dose of study drug (ENVARUS XR), even if the event is not considered to be related to the study drug. Information about all Aes, whether volunteered by the patient, discovered by Investigator questioning, or detected through physical examination, laboratory test or other means, will be collected and recorded on the AE CRF and followed as appropriate.

Abnormal laboratory values or test results constitute Aes only if they induce clinical signs or symptoms, are considered clinically significant, or require therapy. They will be recorded on the AE CRF under the signs, symptoms, or diagnosis associated with them.

As far as possible, each AE will also be described by:

- its duration (start and end dates)
- the severity grade (mild, moderate, severe)
- its relationship to the study drug (suspected / not suspected)
- the action(s) taken and, as relevant, the outcome

Criteria for determining the severity of an AE and its relationship to study drug are shown below in [Table 10-2](#). These criteria are guidelines. It is the responsibility of the Investigator to make a determination of severity and whether or not a relationship to study drug is suspected.

**Table 10-2 AE Severity and Relationship to Study Drug**

| AE Severity          |                                                                                                                                                                                                                                                                                                                                                                         |
|----------------------|-------------------------------------------------------------------------------------------------------------------------------------------------------------------------------------------------------------------------------------------------------------------------------------------------------------------------------------------------------------------------|
| Mild          | Awareness of sign or symptom but easily tolerated.                                                                                                                                                                                                                                                                                                                      |
| Moderate      | Discomfort sufficient to cause interference with normal activities.                                                                                                                                                                                                                                                                                                     |
| Severe        | Incapacitating, with inability to perform normal activities.                                                                                                                                                                                                                                                                                                            |
| AE Relationship      |                                                                                                                                                                                                                                                                                                                                                                         |
| Suspected     | A clinical event, including laboratory test abnormality, with a reasonable time sequence to drug administration, which might or might not be also explained by concurrent disease or other drugs or chemicals.                                                                                                                                                          |
| Not suspected | A clinical event, including laboratory test abnormality judged to be clearly and incontrovertibly due to extraneous causes (diseases, environment, etc.), or with a temporal relationship to drug administration which makes a causal relationship improbable, and/or for which other drugs, chemicals or underlying disease provide a much more plausible explanation. |

Adverse event monitoring and reporting will be followed for the 3-month duration of the study until the AE becomes chronic, or until the patient is deemed “lost to follow-up” by the Investigator or designee.

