| Study Period: 8-month study treatment phase                                                                                                                                                                                                                                                                                                                                                                                                                                                                                                                                                                                                                                                                                                                                                                                                                                                                                                                                                                                                                                                                                                                                                                                                                                                                                                                                                                                                        | Phase of Development: 4 |

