| Methodology:

An open-label, single center, prospective Phase 4 clinical study to assess tacrolimus-induced cognitive outcomes in stable kidney transplant patients converted from oral tacrolimus twice daily immediate-release (TAC-IR) to ENVARSUS XR (tacrolimus extended-release tablets; Veloxis Pharmaceuticals, Inc.) once daily (q.d.). The study is designed to determine if the test drug, ENVARSUS XR, is associated with improved cognitive function relative to that observed with tacrolimus treatment. Each therapy may be concomitantly administered with mycophenolate mofetil (MMF) and/or mycophenolate sodium (MPS), including generic versions of each, as long as doses remain stable during the screening period through Visit 3 of the study. All prophylaxis and other medication will be allowed per standard of care (SOC). Medications that inhibit or induce cytochrome P450 3A (CYP3A) are allowed only if medically necessary, but when using such agents, increased monitoring of tacrolimus drug concentrations is recommended. Stable renal transplant patients are defined as patients who are recipients of a renal transplant 4 weeks to 10 years prior to screening and have received a stable dose (i.e., no dose adjustments) of TAC-IR for a minimum of 4-7 days at the time of screening. Following baseline, study visits will be conducted over a 8-month treatment period with ENVARSUS XR.
 |                                |

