Visit 4 (Month 8± 30 days): Patients will be confirmed to have been on a stable dose of once-daily ENVARSUS XR before Visit 4 assessments are performed. Patients will take their morning dose of ENVARSUS XR and complete the following activities: PGI-I, WHODAS, PIRS-20, and cognitive outcomes assessments (listed above under primary and secondary endpoints). The physician will perform CGI-I. The continuation of ENVARSUS XR will be at the discretion of the patient’s treating nephrologist.

Early Withdrawal Visit: This visit should be scheduled as soon as possible for patients who withdraw from the study. Assessments of concomitant medication use, and AEs will be performed at this visit as well as all visit 3 assessments.

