## 6 STUDY DESIGN

### 6.1 Overall Study Design

This is an open-label, single site, prospective Phase 4 clinical study to assess tacrolimus-induced cognitive impairment in stable kidney transplant patients converted from oral twice-daily TAC-IR to ENVARSUS XR once daily. Approximately 60 adult male or female patients who received a primary or secondary kidney transplant 4 weeks to 10 years prior to study start will be enrolled.

The study design is depicted in [Figure 6-1](#). Patients will be required to have been receiving a stable regimen of TAC-IR (i.e., no dose adjustments) for a minimum of 4-7 days prior to Baseline. At Baseline, patients will be switched to ENVARSUS XR for a total of 3 months.

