### **14.6 Safety Analysis**

#### **14.6.1 Extent of Exposure**

All patients who qualify for the study are expected to receive ENVARSUS XR for 3 months. Duration and total doses of ENVARSUS XR will be summarized for period up to Visit 3 and Visit 4. Reasons for dose change will be listed.

All analyses will be based on Safety analysis dataset.

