#### **14.6.2 Adverse Events**

The Medical Dictionary for Regulatory Activities (MedDRA) will be used to classify all Aes with respect to system organ class and preferred term. Adverse events will be summarized by presenting the number and percentage of patients having any AE, having an AE in each body system, and having each individual AE preferred term. Any other information collected (e.g., severity or relatedness to study drug) will be listed as appropriate. Incidence of Aes/SAEs will be summarized up to Visit 4. All analyses will be based on Safety analysis dataset.

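### Section 10.2.3 ties adverse-event monitoring to a 3-month study, while the schedule runs to Month 8 and Section 14.6.2 reports adverse events to Visit 4; the collection period needs one consistent statement

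*Combined protocol and SAP*

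**What the plan says.** Three places in the current text give 3 months:

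- Section 10.2.3, directly after Table 10-2: "Adverse event monitoring and reporting will be followed for the 3-month duration of the study". The sentence then names two endings that belong to a single event: the event becoming chronic, or the patient being lost to follow-up.
- Section 6.1: "At Baseline, patients will be switched to ENVARSUS XR for a total of 3 months".
- Section 14.6.1: "All patients who qualify for the study are expected to receive ENVARSUS XR for 3 months".

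Other current text gives 8 months. The synopsis describes an "8-month study treatment phase" and says that "study visits will be conducted over a 8-month treatment period with ENVARSUS XR". The synopsis visit list, the Schedule of Study Activities, Section 10.1.4 and Table 10-1 all place Visit 4 at Month 8 with a 30-day window either side.

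The statistical section follows the longer schedule for reporting. Section 14.6.2 states: "Incidence of Aes/SAEs will be summarized up to Visit 4". Section 14.6.1 summarizes duration and total doses to Visit 3 and to Visit 4, although its opening sentence expects 3 months of exposure. Section 6.2.3 names the safety endpoints as the incidence of AEs, of SAEs and of discontinuations due to AEs.

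**The concern.** The period over which AEs are collected and the period over which they are reported should be the same. If site staff take the sentence in 10.2.3 as the end of collection, the Visit 4 incidence table would count only patients with an event in about the first 3 months while presenting the result as incidence to Month 8. A proportion built that way can only be too low. If some patients or staff follow the schedule and others follow 10.2.3, ascertainment differs between patients and the table cannot show it.

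This is more than clerical, because 10.2.3 is the section a site would consult on AE recording and AE incidence is a named endpoint. Section 14.6.1 compounds the problem: its expected exposure disagrees with the visits at which exposure is to be summarized.

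**Working it through.** The plan's own figure is a study duration of 3 months (10.2.3). The check is whether the visit schedule reproduces it.

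**Inputs**
- AE monitoring period: 3 months (10.2.3).
- Visit 3: Month 4 ± 30 days; Visit 4: Month 8 ± 30 days (synopsis, schedule, Table 10-1).
- Anchor for visits: the ENVARSUS XR start day (synopsis, Study Visits) or the enrollment date (Table 10-1). The first dose may be up to 30 days after Visit 2.
- One month is taken as 30.44 days (365.25/12), so 3 months is about 91.3 days.

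**Step 1. Time outside the literal rule, anchored at first dose.** Uncovered time = time to Visit 4 − 3 months.
- Nominal: 8 − 3 = 5 months; 5/8 = 62.5%.
- Earliest Visit 4: 243.5 − 30 = 213.5 days = 7.0 months; uncovered 4.0 months (57%).
- Latest Visit 4: 243.5 + 30 = 273.5 days = 9.0 months; uncovered 6.0 months (67%).

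**Step 2. Anchored at enrollment, with the full 30-day start delay.** Time from first dose to Visit 4 becomes 6.0 to 8.0 months, so the uncovered time is 3.0 to 5.0 months (50% to 62.5%). No variant gives 3 months.

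**Step 3. Position of Visit 3.** Anchored at first dose, the earliest Visit 3 is 121.75 − 30 = 91.75 days, or 3.01 months, just after a 3-month stop. Anchored at enrollment with a 30-day delay, the nominal Visit 3 falls at the same 91.75 days after first dose; only a visit early in its window could come sooner (121.75 − 30 − 30 = 61.75 days, or 2.03 months). So at nominal dates the literal rule ends before the first scheduled post-conversion visit.

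**Step 4. Person-time.** If all 60 enrolled patients completed, monitored time would be 60 × 3 = 180 patient-months under the literal rule and 60 × 8 = 480 under the schedule. For the 52 evaluable patients in Section 14.1 it would be 156 and 416.

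**Step 5. What the other provisions require**

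| Place | Provision on AE collection |
|---|---|
| Schedule of Study Activities | Safety monitoring marked at Visits 3 and 4, standard-of-care visits and early withdrawal; a footnote starts collection after the first dose |
| 10.1.4 | AEs evaluated and recorded at Month 8 |
| 10.1.6 | AEs assessed at early withdrawal |
| 10.2.2 | AE assessment closes each visit |
| 10.2.3, definition | Any event after the first dose; no end date |
| 10.2.4 and 16.1.1.2 | SAEs reportable at any time after the first dose and followed to resolution or permanent outcome |
| 14.6.2 | Incidence reported to Visit 4 |

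Against these, the 3-month sentence in 10.2.3 is the outlier. The amendment summary suggests a reason: Visit 4 was once at Month 3 and moved to Month 8, so the 3-month figures look like text that was not updated. This explains the contradiction; the finding does not rest on it.

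**Step 6. Illustration only.** The documents give no expected AE incidence for this study. Assume a constant hazard and a true 8-month incidence p8. Then h = −ln(1 − p8)/8, and the incidence recorded by 3 months is p3 = 1 − exp(−3h). For p8 = 20%, 40% and 60%, p3 = 8.0%, 17.4% and 29.1%.

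**The case against.** The strongest reply is that collection through Visit 4 is already provided for, as the table above shows, and that the sentence in 10.2.3 is not a clean cutoff. Its stated endings concern the course of one event, so it can be read as a follow-up rule for the length of the study with an outdated number in it. There is no visit at Month 3, and a hard stop would require the site to discard events elicited at Visits 3 and 4, against Sections 10.1.3 and 10.1.4. SAEs have their own reporting rule, and reasons for discontinuation are documented on the case report form under Section 8.3.1.

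Most of this stands. A reader might infer that the plan stops AE collection at Month 3, that 10.2.3 alone governs AE monitoring, or that all three safety endpoints are compromised. The documents do not support any of these. The reply does not remove the contradiction, however. The subject of the sentence is monitoring and reporting as well as follow-up, and a 3-month study length disagrees with the schedule on either reading.

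**Conclusion.** The contradiction is in current operative text and should be corrected. The 3 months in 10.2.3, 6.1 and 14.6.1 cannot be reproduced from the visit schedule. Taken literally, the AE rule leaves 5 of 8 nominal months uncovered, or 3.0 to 6.0 months across the visit windows and the two anchors.

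The consequence is a risk of inconsistent or incomplete capture, mainly of non-serious AEs, and it depends on which provision the site follows. If under-collection occurred, incidence to Visit 4 would be understated. The fall from 20% to 8% (or 40% to 17.4%, or 60% to 29.1%) should not be read as an expected bias: it needs a hard stop at Month 3, a constant hazard and incidences that are assumed. It shows only how large the effect could be in that worst case.

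**What to change.** - In Section 10.2.3, state that AE collection runs from the first ENVARSUS XR dose through Visit 4 or the early-withdrawal visit. This matches the schedule, Sections 10.1.4 and 10.1.6, and the reporting horizon in 14.6.2.
- In a separate sentence, give the rule for following an individual AE to its end, so that the follow-up criteria cannot be taken as the collection period.
- Reconcile the 3-month durations in Sections 6.1 and 14.6.1 with the 8-month treatment period in the synopsis and schedule, including the conflict within 14.6.1 itself.

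The cost is a few sentences. AEs are already assessed at Visit 4, so no visit, procedure or patient burden is added, and the safety analysis can stay as counts and percentages of patients. If patients have already passed Month 3, check that the site has been recording AEs beyond that point.

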#### **10.2.4 Serious Adverse Events**

An SAE is an undesirable sign, symptom, or medical condition which:

- is fatal
- is life threatening
- requires or prolongs hospitalization
- results in persistent or significant disability/incapacity
- constitutes a congenital anomaly or a birth defect
- is medically significant, in that it may jeopardize the patient and may require medical or surgical intervention to prevent one of the outcomes listed above

Serious adverse events must be reported to IQVIA, the pharmacovigilance provider for intake of SAE forms contracted by Veloxis, the developer of Envarsus XR, within 24 hours of the occurrence of the event or at least within 24 hours of awareness of an event occurring at any time after the patient receives his/her first dose of study drug (ENVARUSUS XR). The Investigator must complete the SAE form with as much information available at the time of completion and transmit a facsimile notification form to IQVIA.

Events not considered to be SAEs are hospitalizations for:

- treatment which was elective or preplanned for a preexisting condition that is unrelated to the indication under study and did not worsen
- treatment on an emergency, outpatient basis for an event not fulfilling any of the definitions of serious given above and not resulting in hospital admission

